2.1.7 Pharmacogenetics

Serum skeletal muscle RNA expression analysis

Patients qualified for the muscle biopsy procedures will have additional serum samples taken to assess whether any of the mRNA targets identified in muscle are expressed in serum, which could subsequently be assessed as a serum-based marker of Pompe disease. The analysis of novel serum biomarkers will be planned and reported separately.

Plasma circulating microRNA analyses

Plasma samples will be collected and assessed for circulating microRNA concentrations on both the whole-genome and individual gene levels. The analysis of microRNA targets will be planned and reported separately.

2.2 DISPOSITION OF PATIENTS

This section describes patient disposition for both patient study status and the patient analysis populations.

Screened patients are defined as any patients who met the inclusion criteria and signed the informed consent. Patients who enrolled in the extension study, LTS13769, must have signed informed consent for the extension study, and met the additional inclusion/exclusion criteria, with one of the criteria being the completion of the TDR12857 study.

For patient study status, information in the following categories for either TDR12857 or LTS13769 will be presented in the clinical study report:

- Screened patients
- Screen failure patients
- Treated patients
- Completed TDR12857 study
- Patients who entered the LTS13769 study
- Completed LTS13769 study
- Patients who did not complete the study treatment (either in TDR12857 or LTS13769) by main reason

Number and percentage of patients treated in TDR12857 that fall into each category will be presented in a summary table. Percentages will not be calculated for the screened patients and screen failures. Reasons for treatment discontinuation will be supplied in table(s) giving numbers and percentages by study, dose, and patient groups.

A patient is considered lost to follow-up at the end of the study if he/she is not assessed at the last protocol planned visit and if the time from the last successful contact to the last protocol planned visit is greater than 30 days.

All critical or major deviations will be summarized in tables giving numbers and percentages of deviations by patient group.

Additionally, the analysis populations for safety, pharmacokinetics (PK), pharmacodynamics, and efficacy will be summarized by number of patients enrolled in the TDR12857 study:

- Full Analysis (FA) Set
- Safety Analysis Set
- PK/Pharmacodynamics/Efficacy Analysis Set

2.2.1 Randomization and drug dispensing irregularities

Neither the TDR12857 nor the LTS13769 study was randomized.

Drug-dispensing irregularities will be monitored throughout the study and reviewed on an ongoing basis.

All drug-dispensing irregularities will be documented in the clinical study report. Whether any of these constitute a major protocol deviation is deferred to the decision by the clinical team before the database lock.

Drug-dispensing irregularities to be prospectively identified include but are not limited to:

Table 3 - Drug allocation irregularities

Drug allocation irregularities
Erroneous kit dispensation
Kit not available
Patient switched to another site

2.3 ANALYSIS POPULATIONS

Neither the TDR12857 nor the LTS13769 study was randomized. Patients will be analyzed according to the treatment they actually received instead of the intent to treat (ITT) approach.

2.3.1 Full analysis (FA) set

The FA set consists of all patients who received at least 1 complete infusion of IMP. It will be used for efficacy analysis.

2.3.2 Safety analysis set

The safety analysis set consists of all patients who received at least 1 complete infusion of IMP. It will be used as the basis for all safety analyses.

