11 STATISTICAL CONSIDERATIONS

The Sponsor will be responsible for data collection and editing, reviewing, and validating all the information in the eCRFs, statistical analysis, and generation of the clinical report.

Prior to locking the database, all data editing will be complete and decisions regarding the evaluability of all patient data for inclusion in the statistical analysis will be made. The rationale for excluding any data from the statistical analyses will be prospectively defined, and classification of all or part of a patient's data as non-evaluable will be completed and documented before the entire database is locked.

All data collected in this study will be documented using summary tables, figures, and patient data listings.

All summary statistics will be computed and displayed overall and by treatment group and scheduled assessment time point. Summary statistics for continuous variables will include n, mean, standard deviation, minimum, median, and maximum. For categorical variables, frequencies and percentages will be presented. Graphical displays will be provided as appropriate.

Any changes to the statistical analysis will be delineated in the statistical analysis plan.

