11.3 ANALYSIS POPULATIONS

- **Full Analysis Set:** This analysis set consists of all patients who received at least 1 complete infusion of IMP.
- **Safety Analysis Set:** This analysis set consists of all patients who received any amount of IMP and will be used as the basis for all safety analyses.
- **PK/Pharmacodynamics/Efficacy Analysis Set:** All patients without any critical deviations related to IMP administration, and for whom any PK/pharmacodynamic/efficacy data are available, will be included in the PK/pharmacodynamic/efficacy population.

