1.6 STATISTICAL MODIFICATIONS MADE IN THE STATISTICAL ANALYSIS PLAN

The following main modifications have been made in this version of SAP:

- Added Global Lung Initiative (GLI) 2012 reference equations to calculate FVC % predicted values
- Updated immunogenicity analysis. Some revisions of immunogenicity analysis are made to be consistent with integrated immunogenicity analysis plan.
- Added the second equations for calculating reference value for percentage of predicted total distance walked in 6MWT
- Added Algorithm-defined IARs to be consistent with integrated safety analysis plan
- Updated drug compliance definition to be consistent with COMET and mini-COMET studies
- Added K-M analysis for treatment-emergent adverse events
- The Appendix on Potentially Clinically Significant Abnormalities Criteria was updated

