2 STATISTICAL AND ANALYTICAL PROCEDURES

The statistical analysis and reporting will be based on all data from study TDR12857 and its extension study, LTS13769. The baseline value is defined as the last non missing value prior to first TDR12857 treatment, unless otherwise specified. The rebaseline values will be the last non-missing assessment before patients switch to 20 mg/kg dose for LTS-switch patients.

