2.3.4 ADA evaluable set

All enrolled patients who received at least 1 infusion (partial or completed) of avalglucosidase alfa and had at least one ADA sample taken post-baseline after avalglucosidase alfa infusion that is appropriate for ADA testing with a reportable result.

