To evaluate the effect of ADA and NAb on AEs, the number and percentage of patients experiencing any TEAEs, any treatment-emergent SAEs, or any IARs, hypersensitivity (narrow SMQ), and Anaphylactic reaction (narrow SMQ) will be presented by the following sub-categories: 1. ADA status (ever positive, always negative) 2. ADA peak titer category (always negative, peak titer 100-800, 1600-6400, $\geq 12,800$) 3. ADA response type (always negative, transient response (if occur), and persistent responses subcategories: low response, intermediate response, high ADA response and tolerized at defined timepoints. 4. Correlation of frequency of IAR and ADA peak titer. 5. Neutralizing antibody status (always negative, ever positive).

Association of ADA with selected efficacy

Correlation analysis will be performed between immunogenicity (ADA titers, response categories and neutralizing ADA) and FVC, 6MWT, (raw and percent predicted), MIP, MEP.

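### SAP 2.3.2 admits to the safety set only patients with a complete infusion, where Protocol 11.3 admits anyone given any IMP, so a patient with only partial infusions would be left out of the primary safety tables

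*SAP*

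**What the plan says.** Protocol 11.3 keeps two populations apart. The Full Analysis Set requires at least one complete infusion. For the Safety Analysis Set it says: "This analysis set consists of all patients who received any amount of IMP and will be used as the basis for all safety analyses".

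The SAP gives both sets the same entry rule. Section 2.3.1 reads "The FA set consists of all patients who received at least 1 complete infusion of IMP", and section 2.3.2 reads "The safety analysis set consists of all patients who received at least 1 complete infusion of IMP".

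SAP 2.4.5 then applies the safety population to every safety analysis unless otherwise specified. SAP 2.4.5.1 takes it, within patient and dose group, as the denominator for adverse event percentages. Exposure (SAP 2.4.3.1) and deaths (SAP 2.4.5.2) are also summarised on it.

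The ADA evaluable set in SAP 2.3.4 is wider on this point. It takes enrolled patients who "received at least 1 infusion (partial or completed) of avalglucosidase alfa" and who have a reportable post-baseline ADA result.

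On data scope, SAP section 2 says: "The statistical analysis and reporting will be based on all data from study TDR12857 and its extension study, LTS13769".

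**The concern.** Protocol 9.1 makes safety the primary endpoint, and the two governing documents define its population differently. The narrower definition turns on whether an infusion was finished. Protocol 8.8.2 tells the investigator to consider stopping the infusion at once for a severe hypersensitivity or anaphylactic reaction. A patient could thus be excluded from the safety tables because of the kind of event those tables are meant to count.

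Protocol section 11 promises that "Any changes to the statistical analysis will be delineated in the statistical analysis plan". No part of the SAP declares or justifies this change. Its list in section 1.6 opens "The following main modifications have been made in this version of SAP" and does not mention the safety set.

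**Working it through.** The plan gives no figure to reproduce. The check compares the texts and then bounds the size under stated assumptions.

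**1. Is it a real conflict between current texts?** The SAP was signed in March 2020. Protocol Amendments 08 (September 2020) and 09 (December 2020) came later, and neither summary of changes lists an edit to Section 11.3. A later protocol change therefore does not explain the difference.

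**2. Does the rest of the SAP fit its own definition?**

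| SAP rule | When a patient starts to count |
|---|---|
| 2.1.4, treatment epoch | start of the first IMP administration |
| 2.1.4.1, algorithm-defined IAR | start of the infusion |
| 2.3.4, ADA evaluable set | one infusion, partial or complete (plus an ADA result) |
| 2.3.2, safety set | one complete infusion |

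A patient stopped during a first infusion can therefore have a treatment-emergent event and an IAR by the SAP's own rules, yet lie outside the set that tabulates them. The ADA evaluable set is also not contained in the safety set. SAP 2.4.5.6 plans "the number and percentage of patients experiencing any TEAEs, any treatment-emergent SAEs, or any IARs" by ADA status and names no population. Under the default in SAP 2.4.5, an ADA-evaluable patient with only partial infusions would be missing from that table.

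**3. Who could be affected?** Entry to LTS13769 requires completion of TDR12857 (SAP 1.1 and 2.2), so entrants will in practice have had a complete infusion. That leaves patients treated only in TDR12857. The SAP does analyse them: it pools both studies (section 2), tabulates medications for patients who did not continue (2.4.2), and gives visit-window cutoffs for those who never enrolled in LTS13769 (Appendix B).

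**4. How large could the effect be?** The documents give neither the number treated, N, nor the number with only partial infusions. I assume N = 15, 24 or 40 and one excluded patient. Let x be the number of patients with a given event.

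- Excluded patient had the event: incidence goes from x/N to (x − 1)/(N − 1), a fall of (N − x)/(N(N − 1)). This is largest at x = 1, where it equals 1/N.
- Excluded patient did not have it: incidence goes from x/N to x/(N − 1), a rise of x/(N(N − 1)).

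| Assumed N | Largest fall (x = 1) | Fall at x = 5, patient had event | Rise at x = 5, patient had none |
|---|---|---|---|
| 15 | 1/15 = 6.7 points, to 0% | 10/210 = 4.8 points (33.3% to 28.6%) | 5/210 = 2.4 points |
| 24 | 1/24 = 4.2 points, to 0% | 19/552 = 3.4 points (20.8% to 17.4%) | 5/552 = 0.9 points |
| 40 | 1/40 = 2.5 points, to 0% | 35/1560 = 2.2 points (12.5% to 10.3%) | 5/1560 = 0.3 points |

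Because percentages are computed within patient and dose group, the same formulas apply there with a smaller N. The documents give no group sizes, so I give no per-group figure.

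**The case against.** The strongest reply is that the two rules select the same people wherever both documents apply. Protocol 11.3 governs LTS13769, whose patients had already completed an earlier study. The patients at risk were treated only in TDR12857, and Protocol 11.3 never expressly covered them. This stands as a limit on scope. It does not remove the problem, because the SAP itself brings those patients into its pooled safety analysis and then applies the narrower rule to them.

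Second, SAP 2.2 already tabulates treated patients, reasons for not completing treatment, and the size of each analysis set. If treated means any IMP, a shortfall would be visible there, and a patient who stopped for an adverse event would appear in disposition. Protocol 11.5.3 also requires listings of AEs, SAEs and IARs for all patients, and Protocol 10.5 requires all safety observations in the study report. All of this stands, so the patient would not vanish from the report. But a disposition count or a listing does not put the patient's events back into the TEAE, SAE, IAR or death tables.

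Third, several supporting points are soft:

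- SAP 1.6 lists only main modifications in that version, so its silence does not show when the definition arose.
- The stopping guidance in Protocol 8.8.2 belongs to LTS13769, the TDR12857 protocol is not available, and an interrupted infusion may still be completed.
- The ADA table matters only for a patient with a reportable post-baseline sample (the first post-baseline window in Appendix B, Table 3 opens on day 23), and its authors may have meant the ADA evaluable set.

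These points limit what can be said about bias. They leave the mismatch in the definition untouched.

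**Conclusion.** The concern holds. As written, SAP 2.3.2 replaces the protocol's any-exposure rule for the primary-endpoint population with the Full Analysis Set rule, without declaring or justifying it. It can exclude a patient because of the safety outcome being measured. The mismatch in wording is certain. The consequence is conditional: nil if every treated patient completed at least one infusion, and otherwise at most 1/N per excluded patient with an event, under the assumed N above. Neither the existence nor the direction of any bias is shown. The loss is confined to the safety-set summaries, and ADA incidence has its own set. This should be fixed before database lock because it concerns the primary endpoint and costs almost nothing to correct.

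**What to change.** Reword the first sentence of SAP 2.3.2 so that membership requires any amount of IMP, whether the infusion was partial or complete, in line with Protocol 11.3. Leave the Full Analysis Set as it is. Before database lock, report the number of patients in TDR12857 or LTS13769 who received IMP but completed no infusion, so that the effect, possibly zero, is on record. The cost is one sentence in the SAP and one count from the existing infusion records. No new data are needed.

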2.3.3 Pharmacokinetics/pharmacodynamics/efficacy analysis Set

Enrolled patients without any critical deviations related to IMP administration, and for whom any pharmacokinetics/pharmacodynamics/efficacy data are available, will be included for the analyses of PK, PD, and/or efficacy data, respectively.

2.3.4 ADA evaluable set

All enrolled patients who received at least 1 infusion (partial or completed) of avalglucosidase alfa and had at least one ADA sample taken post-baseline after avalglucosidase alfa infusion that is appropriate for ADA testing with a reportable result.

2.4 STATISTICAL METHODS

2.4.1 Demographics and baseline characteristics

Continuous data will be summarized using the number of available data, mean, standard deviation (SD), median, minimum, and maximum for each dose and patient group. Categorical and ordinal data will be summarized using the number and percentage of patients in each dose and patient group.

Parameters described in [Section 2.1.1](#) will be summarized by dose and patient group using descriptive statistics.

P-values on demographic and baseline characteristic data will not be calculated.

No specific description of the safety/efficacy parameters will be provided at baseline. If relevant, the baseline values will be described along with each safety/efficacy analysis.

2.4.2 Prior or concomitant medications

The prior and concomitant medications will be presented for all patients enrolled in TDR12857, whether or not they continued in the extension study LTS13769.

Medications will be summarized by treatment group according to the WHO-DD dictionary, considering the first digit of the anatomic category class (ATC) and the first 3 digits of the ATC class (therapeutic category). All ATC codes corresponding to a medication will be summarized, and patients will be counted once in each ATC category (anatomic or therapeutic) linked to the medication. Therefore patients may be counted several times for the same medication.

The table for prior and concomitant medications will be sorted by decreasing frequency of ATC followed by all other therapeutic classes based on the overall incidence. In case of equal frequency regarding ATCs within each category, alphabetical order will be used.

2.4.3 Extent of investigational medicinal product exposure and compliance

2.4.3.1 Extent of investigational medicinal product exposure

The extent of IMP exposure will be assessed by the duration of IMP exposure, number of infusions, and amount of dose received. The extent of IMP exposure will be summarized in safety population.

Duration of IMP exposure is defined as last dose date – first dose date + 14 day, regardless of unplanned intermittent discontinuations (see [Section 2.5.3](#) for calculation in case of missing or

incomplete data). Duration of IMP exposure will be summarized descriptively as a quantitative variable (number, mean, SD, median, minimum, and maximum). In addition, duration of treatment exposure will also be summarized categorically by numbers and percentages for each of the following categories and cumulatively according to these categories: <6 months, 6 months to <1 year, 1 to <2 years, 2 to <3 years, 3 to <4 years, 4 to <5 years, 5 to <6 years, and \geq 6 years.

The cumulative dose information will be assessed by the total number of infusions received. These data will be summarized descriptively.

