6.2 DURATION OF STUDY PARTICIPATION

6.2.1 Duration of study participation for each patient

The duration of the study for each patient is initially 6 years. Each patient will continue with the study until the patient withdraws, the Investigator withdraws the patient, or the Sponsor terminates the study. An additional follow-up phase will begin after the patient has completed the 6-year study period, and will last until avalglucosidase alfa is approved in the patient's country, except in the UK, Germany and Denmark, where the duration of the additional follow-up phase will be up to the approval in the country or limited to a maximum of 2 years, whichever occurs first (ie, for patients in the UK, Germany and Denmark, the total study duration per patient is 8 years at the maximum including the initial 6-year period and the additional 2-year follow-up) (refer to Appendix 1 [[Section 17.1](#)] for definition applicable for patients in the UK, Germany and Denmark).

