11.9 EXTENT OF STUDY TREATMENT EXPOSURE AND COMPLIANCE

Number of weeks in the study, the number of study infusions, and the dose received by patients will be summarized using summary statistics. Frequency and percentage of patients remaining on treatment will be summarized quarterly.

Data from all patients who are enrolled in the study will be included in the summary of patient accountability. The frequency and percentage of patients who are enrolled in the study, discontinued from the study, and completed the study, along with reasons for discontinuation, will be summarized.

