1 OVERVIEW AND INVESTIGATIONAL PLAN

1.1 STUDY DESIGN AND RANDOMIZATION

LTS13769 is an open-label, multicenter, and multinational extension study with repeated IV infusions of avalglucosidase alfa. Safety, pharmacokinetic, pharmacodynamic, pharmacogenetic, and exploratory efficacy data will be collected during this long-term study. The population will be patients with Pompe disease who have completed study avalglucosidase alfa TDR12857. Patients who received avalglucosidase alfa intravenous (IV) infusion 20 mg/kg of body weight every other week (qow) in the TDR12857 study will continue to receive the same dose in the extension study, while patients who previously received the 5 or 10 mg/kg qow dose will first continue on the same dose that they received in the TDR12857 study, and then provide consent to switch to the 20 mg/kg qow regimen for the remaining duration of the LTS13769 study (henceforth called the LTS-switch group in this document).

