2.4.3.2 Compliance

A given administration will be considered noncompliant if the patient did not take the planned dose (eg, missed dose, overdose, or underdose) of treatment as required by the protocol. No imputation will be made for patients with missing or incomplete data.

Compliance is calculated as the total amount of drug actually taken by a patient divided by the total amount of drug expected to be taken multiplied by 100. The number and percentage of patients with noncompliance (missed 2 or more consecutive infusions, or missed \geq 20% of total doses in the treatment or extension period) will be provided.

Treatment compliance will be summarized descriptively as quantitative variables (number, mean, SD, median, minimum, and maximum). The percentage of patients whose compliance is <80% will be summarized.

Additional dose related non-compliance will be summarized as protocol deviations.

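### The SAP's only rule for cumulative dose is a count of infusions, although dose per infusion is 5, 10 or 20 mg/kg and changes within LTS-switch patients

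*SAP*

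**What the plan says.** SAP 2.4.3.1 opens with three exposure measures: "The extent of IMP exposure will be assessed by the duration of IMP exposure, number of infusions, and amount of dose received". It defines duration in detail. On dose it gives a single rule: "The cumulative dose information will be assessed by the total number of infusions received". It defines no variable in mg or mg/kg.

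Protocol 11.9 treats count and dose as separate items: "Number of weeks in the study, the number of study infusions, and the dose received by patients will be summarized using summary statistics".

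Dose per infusion is not constant. Under SAP 1.1, "patients who previously received the 5 or 10 mg/kg qow dose will first continue on the same dose" as in TDR12857, and they then consent to "switch to the 20 mg/kg qow regimen for the remaining duration of the LTS13769 study". SAP section 2 combines the two studies: "The statistical analysis and reporting will be based on all data from study TDR12857 and its extension study, LTS13769". An LTS-switch patient's total therefore spans two dose levels.

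The amount given is already needed elsewhere. SAP 2.4.3.2 says: "Compliance is calculated as the total amount of drug actually taken by a patient", divided by the amount expected.

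**The concern.** An infusion count stands in for cumulative dose only if every infusion carries the same dose. Here dose differs between patients and, in the LTS-switch group, within a patient. A programmer who follows the one operative sentence would label a count as cumulative dose and would leave the third listed measure, amount of dose received, without a definition. The dose summary required by Protocol 11.9 might then not be produced. Protocol section 11 says that changes to the analysis will be set out in the SAP, but the main modifications listed in SAP 1.6 do not mention replacing dose received by a count.

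What is at stake is the description of exposure in a study whose primary objective includes long-term safety. SAP 2.4.5.1 splits several adverse event tables for LTS-switch patients at re-baseline, but 2.4.3.1 plans no matching split of exposure. A reader of those tables would not see how much drug lay behind each period.

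**Working it through.** The documents give no cumulative dose figure, so there is nothing to reproduce. The check asks how far patients with the same infusion count can differ in dose.

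**Inputs from the documents**
- Dose levels of 5, 10 and 20 mg/kg every other week, with a switch to 20 mg/kg (SAP 1.1).
- LTS13769 duration: "The duration of the study for each patient is initially 6 years" (Protocol 6.2.1).

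**Assumptions**
- 13 infusions in TDR12857 (Weeks 1 to 25, every other week).
- 26 infusions a year in LTS13769, so 6 × 26 = 156.
- No infusion missed or incomplete.
- The switch month is not stated, so a range is shown.

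Total count: 13 + 156 = 169. On 20 mg/kg throughout: 169 × 20 = 3380 mg/kg.

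**Formulas**, for a starting dose d and a switch at LTS month m:
- infusions before the switch = 13 + 26 × m / 12
- infusions after the switch = 169 − infusions before
- cumulative dose = before × d + after × 20
- ratio = 3380 / cumulative dose

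Example, d = 5 and m = 36: before = 13 + 78 = 91 and after = 78. Dose = 91 × 5 + 78 × 20 = 455 + 1560 = 2015 mg/kg. Ratio = 3380 / 2015 = 1.68.

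| Assumed switch (LTS month) | Infusions before / after | 5 mg/kg starter: mg/kg (ratio) | 10 mg/kg starter: mg/kg (ratio) |
|---|---|---|---|
| 6 | 26 / 143 | 2990 (1.13) | 3120 (1.08) |
| 12 | 39 / 130 | 2795 (1.21) | 2990 (1.13) |
| 24 | 65 / 104 | 2405 (1.41) | 2730 (1.24) |
| 36 | 91 / 78 | 2015 (1.68) | 2470 (1.37) |
| 48 | 117 / 52 | 1625 (2.08) | 2210 (1.53) |
| 60 | 143 / 26 | 1235 (2.74) | 1950 (1.73) |

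Every row has the same count of 169, so the SAP's measure cannot tell the rows apart. The problem also arises inside the LTS-switch group: two 5 mg/kg starters who switch at months 6 and 36 differ by 2990 / 2015 = 1.48.

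**Upper bound.** A patient who never leaves 5 mg/kg gives 20 / 5 = 4.0 against a 20 mg/kg patient with the same count; at 10 mg/kg the bound is 20 / 10 = 2.0. A 5 mg/kg patient with TDR12857 data only would show 13 × 5 = 65 against 13 × 20 = 260 mg/kg.

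**Where it appears.** In a column where every infusion is at one known dose, count × dose recovers the mg/kg total, apart from incomplete infusions. The distortion therefore falls mainly on the LTS-switch group and on any overall column, which Protocol section 11 foresees.

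**The case against.** The strongest reply is that dose received is already planned. It is the third measure in the opening sentence of SAP 2.4.3.1, Protocol 11.9 requires it, and the compliance calculation uses actual amounts. On this view one sentence is badly worded and exposure does not rest on counts alone. That stands as a limit on the point: the defect is an inconsistency and an undefined variable. It does not remove the defect, because the only rule given for cumulative dose is still the count.

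Second, the number of infusions is a valid exposure measure in its own right. That also stands; only its use as cumulative dose is wrong.

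Third, safety results are presented by dose and patient group (SAP 2.4.5), and the before- and after-rebaseline periods are defined in SAP 2.1.4, so the dose change is visible elsewhere. This is largely right and narrows where the distortion can appear. However, 2.4.3.1 does not itself say that the exposure table has those columns or that split.

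Fourth, no other planned result depends on cumulative dose. Adverse event percentages use the number of patients in the safety population, the Kaplan-Meier summary uses 6-month intervals, and no dose-adjusted rate is specified. This stands in full.

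A reader might infer that the exposure figures could be out by a factor of four. Over a long series the plan does not support that, because 5 and 10 mg/kg patients are to move to 20 mg/kg. A patient who never switched would most plausibly have left early, with a short series.

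**Conclusion.** The point holds as an inconsistency with a wrong operative rule, and it is minor. The SAP lists amount of dose received, the Protocol requires it, and the SAP then measures cumulative dose by a quantity that ignores dose.

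Against a patient on 20 mg/kg throughout with the same 169 infusions, the difference in mg/kg is a factor of 1.13 to 1.68 for a 5 mg/kg starter who switches between LTS months 6 and 36, and 2.74 at month 60. For a 10 mg/kg starter it is 1.08 to 1.73 over months 6 to 60. These figures rest on the assumed infusion schedule, full infusions and assumed switch months. Four-fold is only the bound for a 5 mg/kg patient who never switched.

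Incomplete infusions, which Protocol 8.7.1 says are to be considered in the analysis, would add differences that a count may miss; the documents give no basis for sizing them. It would also go too far to infer that the safety results are biased: the exposure summary changes, but no adverse event percentage or Kaplan-Meier estimate does.

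**What to change.** Replace the sentence in SAP 2.4.3.1 with a definition along these lines: cumulative dose is the sum, over all infusions in TDR12857 and LTS13769, of the amount actually administered in mg/kg. Summarize it by dose and patient group and, for LTS-switch patients, separately before and after re-baseline. State that this is the amount of dose received named in the section's opening sentence and the dose received of Protocol 11.9. Keep the number of infusions as its own variable.

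The cost is a short SAP edit and a few extra rows in the exposure table. No new data are needed: the eCRF holds the dosing information (Protocol 8.7.1), the compliance calculation already needs actual amounts, and body weight is collected for expressing them per kilogram. The SAP should say which weight is used; Protocol 8.1 bases the dose calculation on the most recent one.
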